20.0 Withdrawal of Subjects

N/A: This study is not enrolling subjects. This section does not apply.

20.1 Describe anticipated circumstances under which subjects may be withdrawn from the research without their consent.

Response: Subjects may be withdrawn due to failure to comply with study protocol, or pursuing of treatments incompatible with study procedures (e.g., home instruction).

20.2 Describe any procedures for orderly termination.

NOTE: Examples may include return of study drug, exit interview with clinician. Include whether additional follow up is recommended for safety reasons for physical or emotional health.

Response: At the end of the school year, all participants will be invited to an exit interview, complete ratings of effectiveness and satisfaction, and review study outcomes with the investigators. Recommendations for continued treatment will be provided.

20.3 Describe procedures that will be followed when subjects withdraw from the research, including retention of already collected data, and partial withdrawal from procedures with continued data collection, as applicable.

Response: If participants withdraw from the research, any data collected up until that point will be retained. If a participant withdraws from a particular part of the protocol (e.g., declines school intervention) other procedures and assessments will continue, if the participant agrees to continued participation in other aspects of the study.

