idiosyncratic to address the heterogeneity that is typical in samples of children with ADHD. For example, a child with an IEP due to low achievement in reading, who also exhibits disruptive behaviors and noncompliance, might have targets established such as “Completes assigned reading tasks with 80% or better accuracy;” “Interrupts class discussion 4 or fewer times per class/interval;” and “Has 2 or fewer instances of noncompliance during the transition to lunch.” A standard list of common DRC goals has been created and will be used to facilitate initial target behavior selection. These goals clearly overlap with the actual goals created as part of the development project ([name] et al., 2010). The DRC would be evaluated and completed by the teacher daily, and feedback will be provided to the child throughout the day on progress made toward DRC goals.

At the end of each day, the teacher will send the DRC home with the child so that the parent is provided feedback on a daily basis regarding the child’s behavior at school. Parents will attend three individual parent training meetings to introduce them to the DRC also conducted in January in the child’s school, and they will establish home-based rewards contingent on the child’s DRC performance. For example, for a child with three DRC goals evaluated twice per day (i.e., before lunch and before dismissal), there are six possible “yes’s.” A given parent might remove computer access for this child previously provided non-contingently and only provide 10 minutes for each “yes” reported for the day (i.e., a child who earned all “yes’s” on a particular day would be rewarded with 60 minutes of computer time). This binary approach of yes/no is easier to explain to the child, and permits the child to track his/her own progress across the day (i.e., number of yes’s earned), relative to a continuous rating, which may be harder for the child to comprehend/quantify. In addition to the home-based contingency management based on school feedback, which makes the child accountable at home for school-based behavior, the DRC serves as a mechanism of daily communication between the parent and teacher. Given the variability in behavior expected with a child with ADHD, such daily communication is often crucial for preventing deterioration in functioning and presents the parent and teacher with multiple opportunities to problem-solve.

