called/texted the next morning and the child and parent will be asked what contingencies were administered based on school behavior. In addition, teachers will be asked in the SAU and DRC groups about the provision of any school-based rewards. SAU

parents will also be asked whether they received any feedback from the teacher regarding the child's behavior in school that day and in what form (email, DRC, etc.).

In addition, for participants in the DRC group, parents will be asked each day to sign the DRC and record the reward administered, if any. Then, they will return the DRC to the teacher the next morning. This

will help promote home-school communication, and was a procedure used successfully in the Goal 2 project. It is hypothesized that the phone calls to query reward administration will replicate and extend these preliminary findings. Such phone calls have been successfully implemented by our lab on other funded projects (e.g., [name], et al., 2012; NIMH # R34MH078051). The interface between observations of primary outcome and observations of integrity/fidelity during the course of the study is illustrated above. Finally, parents/teachers in both groups will complete a checklist at post-treatment reporting how often they used the components of the DRC intervention (i.e., provided home reward; daily feedback).

Observations for Primary Outcome	Month	Observations for Integrity/Fidelity
SBTR Completed by Observer Blind to Condition (3 total)	January	Integrity/Fidelity Observation(1 total)
N/A	February	Integrity/Fidelity Observation(1 total)
N/A	March	Integrity/Fidelity Observation(1 total)
N/A	April	Integrity/Fidelity Observation(1 total)
SBTR Completed by Observer Blind to Condition (3 total)	May	Integrity/Fidelity Observation(1 total)

10.3 List any instruments or measurement tools used to collect data (e.g. questionnaire, interview guide, validated instrument, data collection form).

Include copies of these documents with your submission.

Response: See description in 10.2 above. In addition, a table of measures and administration schedule is included with the submission.

10.4 Describe any source records that will be used to collect data about subjects (e.g. school records, electronic medical records).

Response: N/A

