17.0 Data Management and Analysis

17.1 Describe the data analysis plan, including any statistical procedures. This section applies to both quantitative and qualitative analysis.

Response: To ensure appropriate manipulation of the independent variable the treatment integrity data described above will be collected and analyzed. The distributional characteristics of all dependent variables will be examined. If outcomes are appreciably non-normal, we will consider power transformations where appropriate. Although we expect that our cross-site and cross-cohort training efforts will mitigate the possibility of any site, cohort, or consultant differences, we will still conduct sensitivity analyses that evaluate treatment effects separately by cohort, site, and

consultant. As the study is powered for efficacy analyses and we do not anticipate being powered to detect cohort/site/consultant effects, these analyses will emphasize effect size comparisons. To the extent that any differences are revealed, we will improve cross-site and cross-cohort training and fidelity observations, as well as to consider the inclusion of site, cohort, or consultant as additional covariates. Benjamini-Hochberg adjustments will be used throughout in order to control for the false discovery rate associated with multiple comparisons across outcomes (Benjamini & Hochberg, 1995). This strategy is implemented in SAS® using PROC MULTTEST. Multiple imputation methods will be used to accommodate missing data (Allison, 2002). This strategy is implemented in SAS® using PROC MI and MIANALYZE.

Aim 1. Investigate the effectiveness of using a DRC to link the child with ADHD's IEP to daily classroom behavior.

Aim 1 will be evaluated using Analysis of Covariance (ANCOVA) models of the following form

$$y_{post} = \gamma_1 \text{pretest} + \gamma_2 \text{DRC} + \sum_{j=1}^5 \gamma_j \text{covariates} + e_i$$

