Risk: Randomization to the treatment arms. **Procedure:** This risk will be addressed through the informed consent/assent process, where parents and children will agree to be assigned to treatment groups. Parents and children are free to withdraw from the study at any time and are not obligated to participate in the treatment group to which they are assigned. Withdrawing from this study will not affect any future interactions or their participation in any future clinical services or studies at the FIU or the UB centers.

Risk: Participants may experience a worsening of ADHD if ADHD medication is withheld for the study assessments. **Procedure:** Only those participants who obtain permission from the prescribing physician will have medication withheld. This is a procedure common in studies of ADHD treatment ([name] et al., 2010; [name], Wheeler, & Chronis, 1998).

21.2 *Describe procedures performed to lessen the probability or magnitude of risks, including procedures being performed to monitor subjects for safety.*

Response: See 21.1

21.3 *If applicable, indicate which procedures may have risks to the subjects that are currently unforeseeable.*

Response: There are no procedures included for which there are unforeseeable risks.

21.4 *If applicable, indicate which research procedures may have risks to an embryo or fetus should the subject be or become pregnant.*

Response: N/A

21.5 *If applicable, describe risks to others who are not subjects.*

Response: N/A

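### Section 20.1 permits removal from the research for non-compliance without securing the May outcomes; if removals fall more on the DRC arm, imputation could modestly overstate the effect

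*Combined protocol and SAP*

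**What the plan says.** Section 20.1 answers a template question about removing subjects who have not agreed to leave: "Subjects may be withdrawn due to failure to comply with study protocol". Its other ground is taking up treatment incompatible with the study, with home instruction as the example. Compliance is not defined and no arm is named.

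Section 20.3 has two sentences. The first is: "If participants withdraw from the research, any data collected up until that point will be retained". The second concerns a participant who withdraws from one part of the protocol, such as declining the school intervention. In that case "other procedures and assessments will continue, if the participant agrees to continued participation in other aspects of the study". Section 20.2 invites all participants to a year-end exit interview with effectiveness and satisfaction ratings. Section 21.1 adds that families "are not obligated to participate in the treatment group to which they are assigned".

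On family tasks, section 10.1 says of the DRC arm: "Parents will attend three individual parent training meetings to introduce them to the DRC". Section 10.2 says: "for participants in the DRC group, parents will be asked each day to sign the DRC and record the reward administered, if any". For SAU, section 10.1 lists an initial and then monthly consultant meetings with the teacher, and no daily family task.

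On missing data, section 17.1 says: "Multiple imputation methods will be used to accommodate missing data". It gives no imputation model and no sensitivity analysis. Section 17.2 says that all 216 participants contribute to each analysis. Section 21.1 quotes attrition under 5% in the two centers' programs, not split by arm.

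**The concern.** Removal under 20.1 is from the research, not only from the intervention, and nothing secures the May assessment afterwards. If the children removed are mostly in one arm and mostly those who gained least, their missing outcomes are not missing at random given arm and pretest. Imputation would then give them values typical of the children who stayed, and the estimate would drift from the effect in all randomised children toward the effect in those who kept up with the DRC. An outcome that was never collected cannot be recovered at analysis, so the wording has to be settled before removals happen.

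**Working it through.** **Step 1. Which rule governs a non-compliant child?** Take a DRC family that stops attending meetings and signing cards but has not asked to leave.
- Under 20.1 the team may withdraw the child from the research. The first sentence of 20.3 then keeps earlier data and is silent on May.
- Under the second sentence of 20.3, the same family could be treated as having declined part of the protocol, and assessments continue.
- Under 21.1 the family had no duty to take part in its assigned group.

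Nothing says which rule prevails. The exit ratings in 20.2 are not the SBTR observations or the teacher scales such as the APRS.

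**Step 2. Would removal be related to arm and outcome?** The DRC family tasks (three meetings, a daily signature, home rewards) have no listed SAU counterpart. Section 10.2 reports that, in the Goal 2 project, the percentage of DRCs rewarded appropriately correlated -.53 (p = .002) with end-of-year disruptive behavior; no adjustment for pretest is reported. Section 10.2 also expects classroom environment, teacher feedback and home consequences together to mediate the effect fully. On that theory a child in whom none of the three changes gains nothing, while a lapse at home alone removes only part of the benefit.

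**Step 3. Reproduce the plan's own figure.** Section 17.2 gives d = .50, covariate R² = .45, power .80 and N = 71. Alpha is not stated; assume .05, two-sided.

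Total N = 4 × (1 − .45) × (1.960 + 0.842)² / .50² = 69.1, or 70 in two equal groups. The noncentral t gives 72, and power at N = 71 is .80. The inputs reproduce, so d = .50 and R² = .45 are used below.

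**Step 4. Size of the bias.** Let
- w = share of the DRC arm removed, with no SAU removals (assumption);
- d_c = .50, the effect in DRC children who stay;
- d_n = the effect in removed children (assumption);
- u = how much better (+) or worse (−), in SD, children prone to non-compliance do than the pretest predicts, in either arm (assumption).

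As-randomised effect = (1 − w) × d_c + w × d_n. If the imputation model holds arm and pretest but no compliance information, removed DRC children are imputed like those who stay, and

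bias = w × (d_c − d_n − u).

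Two values of w can be tied to the documents. One is 5%, the quoted attrition ceiling applied to the DRC arm. The other is 10%: .05 × 216 = 10.8, about 11 children, all among the 108 in DRC.

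| d_n | u | Bias, w = 5% | Bias, w = 10% |
|---|---|---|---|
| 0 | 0 | 0.025 | 0.05 |
| .25 | 0 | 0.013 | 0.025 |
| .50 | 0 | 0 | 0 |
| 0 | −.3 | 0.04 | 0.08 |
| .50 | +.3 | −0.015 | −0.03 |

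In the first row the as-randomised effects are .95 × .50 = .475 and .90 × .50 = .45, so the relative inflation is .025/.475 = 5% and .05/.45 = 11%.

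A simulation of the ANCOVA with multiple imputation (108 per arm, R² = .45, 10 imputations) agrees. It gave 0.025 and 0.052 for the first row, 0.001 and 0.000 for the third, 0.040 and 0.081 for the fourth, and −0.016 and −0.030 for the fifth.

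**The case against.** The case for leaving the text alone is substantial.

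- **Non-adherence is partly covered.** The example in 20.3 is a family that declines the school intervention, and it stays in assessment. Section 21.1 frees families from taking part in the assigned group. Aim 3 uses home-reward accuracy and teacher feedback as mediators, so the investigators have reason to keep poor adherers. This stands as evidence of intent, but the sentence in 20.3 addresses a participant's own choice, not removal by the team.
- **The rule is discretionary and names no arm.** Much of the DRC workload falls on teachers, who under 26.2 are not the participants. Monthly consultant meetings occur in both arms, and home instruction can arise in either. This stands: imbalance is an inference from the family tasks, not something the documents state.
- **No complier analysis is planned.** Section 17.2 has all 216 contribute, and no per-protocol set is defined. This stands. However, a removed child contributes an imputed May value, not an observed one.
- **The imputation model is open.** Integrity data gathered before removal could inform it. That is possible, but the plan does not say so.
- **Large inflation has no source.** Removing 20% of the DRC arm with no benefit in any of them would give .10 on .40, or 25%. A reader might infer inflation on that scale, but no removal rate near 20% appears in the documents.

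**Conclusion.** The point holds as a gap that can produce selective loss of May outcomes. Sections 20.1 and 20.3 overlap on a non-compliant child and need to be reconciled. Removals would probably, not certainly, fall more on the DRC arm and on children with less benefit.

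With all removals in DRC and no benefit in those removed, the overstatement is about 0.025 SD at 5% DRC removal and about 0.05 SD if all of a 5% overall attrition fell there. It reaches about 0.08 SD if those children also do 0.3 SD worse than the pretest predicts. It is zero if they benefit equally, and negative if they also do better than predicted. Aim 1 power is not at issue: at an as-randomised effect of .45 and N = 216 it is still about .99.

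A reader might infer that 20.1 ends outcome collection mainly in the DRC arm, inflates the effect and turns the trial into a comparison of compliers. The documents do not support that. They do not say that assessment stops after removal, give no removal rate by arm, and do not establish that removed children would do worse than imputed.

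**What to change.** Amend 20.1 and 20.3 so that neither non-compliance nor a change of setting is a reason to end data collection. For every randomised child, seek the May SBTR observations (where the child still attends a classroom) and the teacher and parent ratings, unless the family itself withdraws from data collection. Make clear which sentence of 20.3 applies when the study team, not the family, initiates the change. This concerns data collection only and leaves intervention decisions as they are.

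In 17.1, state that the 216 children whom 17.2 says contribute are analysed in the arm to which they were randomised, whatever their compliance.

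The cost is a few sentences in three sections and May assessments for a few more children, all within the planned 216.

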21.0 Risks to Subjects

21.1 List the reasonably foreseeable risks, discomforts, hazards, or inconveniences to the subjects related to their participation in the research. Consider physical, psychological, social, legal, and economic risks. Include a description of the probability, magnitude, duration, and reversibility of the risks.

NOTE: Breach of confidentiality is always a risk for identifiable subject data.

Response: **Risk:** Participants may experience mild and transitory psychological discomfort from completing research measures, including reporting on child emotional and behavior problems and academic difficulties. **Procedure:** Participants and their parents will be advised to ask questions of study personnel if confidentiality is of a concern, and to refrain from answering questions that cause them personal distress.

Risk: Participants may face risk as they may experience mild and transitory psychological discomfort from changing their behaviors as part of the study interventions. **Procedure:** The centers at FIU and at UB are quite experienced at running psychosocial intervention for youth with ADHD in school and with parents. We experience very low attrition rates (under 5% from our clinical and research programs). None the less, children and parents can refuse to continue to participate in the study at any time.

Risk: Teachers may find the additional consultation and implementation of new strategies to be burdensome. **Procedure:** We are quite experienced in teacher consultation both in IES- and NIH-funded studies and in nonresearch work in the Buffalo and Miami-Dade schools. Our groups are well known to teaching staff, given that we provide regular inservice instruction and consultation to the districts, and we have excellent rapport with principals, teachers, psychologists/social workers, and administrators. We have had very low rates of teacher refusal to participate in the studies, and we anticipate that to continue for

this project. Indeed, the vast majority of teachers find the consultations to be helpful in coordinating school-based supports for their students with ADHD. We will work with teachers to schedule consultations at times teachers identify as most convenient. Furthermore, consultations are intended to be collaborative and teachers' input is encouraged.. Efforts will be made to collaborate with and reengage teachers who refuse to contribute to any specific intervention or study activity.

Risk: Randomization to the treatment arms. **Procedure:** This risk will be addressed through the informed consent/assent process, where parents and children will agree to be assigned to treatment groups. Parents and children are free to withdraw from the study at any time and are not obligated to participate in the treatment group to which they are assigned. Withdrawing from this study will not affect any future interactions or their participation in any future clinical services or studies at the FIU or the UB centers.

Risk: Participants may experience a worsening of ADHD if ADHD medication is withheld for the study assessments. **Procedure:** Only those participants who obtain permission from the prescribing physician will have medication withheld. This is a procedure common in studies of ADHD treatment ([name] et al., 2010; [name], Wheeler, & Chronis, 1998).

21.2 *Describe procedures performed to lessen the probability or magnitude of risks, including procedures being performed to monitor subjects for safety.*

Response: See 21.1

21.3 *If applicable, indicate which procedures may have risks to the subjects that are currently unforeseeable.*

Response: There are no procedures included for which there are unforeseeable risks.

21.4 *If applicable, indicate which research procedures may have risks to an embryo or fetus should the subject be or become pregnant.*

Response: N/A

21.5 *If applicable, describe risks to others who are not subjects.*

Response: N/A

22.0 Potential Benefits to Subjects

22.1 Describe the potential benefits that individual subjects may experience by taking part in the research. Include the probability, magnitude, and duration of the potential benefits. Indicate if there is no direct benefit.

*NOTE: Compensation **cannot** be stated as a benefit.*

Response: All participants in the study will have monitoring of school-based treatments, which may help inform future treatment efforts and decisions. Participants in the DRC condition will have evidence-based interventions for ADHD (i.e., behavior therapy) delivered which may directly benefit the functioning of the participants in schools.

23.0 Compensation for Research-Related Injury

- N/A:** The research procedures for this study do not present risk of research related injury (e.g. survey studies, records review studies). This section does not apply.

23.1 If the research procedures carry a risk of research related injury, describe the available compensation to subjects in the event that such injury should occur.

Response:

23.2 Provide a copy of contract language, if any, relevant to compensation for research related injury.

*NOTE: If the contract is not yet approved at the time of this submission, submit the current version here. If the contract is later approved with **different language regarding research related injury**, you must modify your response here and submit an amendment to the IRB for review and approval.*

Response:

